10.3.2.1 Visit 5 (Day 29 ± 3, first day of Cycle 2)

The following procedures will be performed at Visit 5:

- Review medical history.
- Record concomitant medications including start/stop dates, indication, dose, toxicities, and frequency taken after Visit 4.
- Measure and record weight.
- Record vital signs. Measure body temperature, systolic / diastolic BP, and pulse rate.
- Assess and record performance status (ECOG).
- PART A only: Tissue biopsy (required unless investigator and medical monitor deems collection inadvisable).
- PART A only: Collect blood samples for ctDNA.
- Collect blood samples for blood chemistries, hematology, and creatinine clearance.
- Collect urine samples for urinalysis.
- Perform urine pregnancy test for female patients who are not postmenopausal or surgically sterile. If urine test is positive, collect blood for a serum pregnancy test. If serum pregnancy test is positive, withdraw patient from study and contact the medical monitor.
- Assess and record AEs.
- Obtain all unused study drug from patient.
- Assess study drug compliance by reviewing pill count.
- Assess and record disease status (every 2 cycles).
- Dispense study drug supply for self-dosing. Extra doses may be dispensed at the investigator's discretion to ensure continuous dosing.

10.3.2.2 Visit 6 and 7

Cycle 2 visits 6 and 7 procedures are similar to Cycle 1 visit 3, although no pharmacokinetic or pharmacodynamic measurements will be made unless specifically requested by investigator or the patient changes dose level.

10.3.3 Cycle 3 and Subsequent Cycles Visit (Day 1 ± 3 of each cycle)

Cycle 3 and subsequent cycles have one scheduled visit per cycle. No pharmacokinetic or pharmacodynamic measurements will be made unless specifically requested by the investigator or the patient changes dose level.

The following procedures will be performed at the Cycle 3 and Subsequent Cycles Visit:

- Review medical history.
- Record concomitant medications including start/stop dates, indication, dose, toxicities, and frequency taken since previous visit.
- Measure weight.
- Record vital signs. Measure body temperature, systolic / diastolic BP, and pulse rate.
- Assess and record performance status (ECOG).
- Collect blood samples for blood chemistries, hematology, and creatinine clearance.
- Collect urine samples for urinalysis.

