### **N**

N will be the number of patients in the specified population and group.

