### **Categorical data**

Categorical data will be summarized using n and percentage.

- All categories will be presented, even if no patients are counted in a particular category, unless otherwise stated.
- A Missing category will be displayed in all tables for categories where at least one missing value exists, unless otherwise specified.
- Counts of zero in any category will be presented without percentage.
- All summary percentages will be calculated using N, unless otherwise stated in a footnote.
- For AEs, medical history, prior and concomitant medications, the counts are based on single counts of patients with multiple events/treatments under the same category, while the percentages are calculated using N. Counts will be displayed by descending order of frequency for the overall group by dictionary hierarchy.

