### Safety Analysis Set

The safety analysis set will consist of all patients who received at least one dose of study drug. This analysis set will be used for all safety analyses.

For Part B, analyses performed on the safety population will allocate patients' treatment group as actually received.

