## 9.9 SAFETY DATA ENDPOINTS AND ANALYSES

All safety analyses will be performed on the Safety Analysis Set using descriptive statistics.

All safety data will be presented by group and overall, for both Part A and Part B, unless otherwise specified in the specific section.

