### 9.9.1 Adverse Events (AEs)

The following definitions will be used:

- **Treatment-emergent AEs (TEAEs):** Treatment-emergent adverse event (TEAE) is defined as any AE that emerges during on-treatment period, after the 1st dose of the study agent.
- **Related AEs:** AEs suspected by the Investigator and/or Sponsor to have a relationship to study treatment (as recorded on the AE eCRF page, Causality = Related, Possibly Related, or missing).
- **Serious Adverse Events (SAE):** serious AEs (as recorded on the AE eCRF page, Does AE Meet the Definition of an SAE = Yes).
- **AEs leading to treatment discontinuation:** AEs leading to permanent discontinuation of study treatment (as recorded on the AE eCRF page, Action taken with study treatment = Drug withdrawn).
- **AEs leading to dose reduction:** AEs leading to dose reduction of study treatment (as recorded on the AE eCRF page, Action taken with study treatment = Dose Reduced).
- **AEs leading to treatment interruption:** AEs leading to treatment interruption of study treatment (as recorded on the AE eCRF page, Action taken with study treatment = Drug Interrupted).
- **AEs leading to Death:** adverse event leading to death (as recorded on the AE eCRF page, Results in death, or Outcome = Fatal, or Grade = 5).

An overview summary table will present the number and percentage of patients with a TEAE, including:

- TEAEs / TEAEs related to study treatment

- SAEs / SAEs related to study treatment
- TEAEs leading to treatment discontinuation / TEAEs related to study treatment leading to treatment discontinuation
- TEAEs leading to treatment discontinuation within 1 cycle / TEAEs related to study treatment leading to treatment discontinuation within 1 cycle
- TEAEs leading to treatment discontinuation following 1 cycle / TEAEs related to study treatment leading to treatment discontinuation following 1 cycle
- TEAEs leading to treatment interruption / TEAEs related to study treatment leading to treatment interruption
- TEAEs leading to treatment interruption within 1 cycle / TEAEs related to study treatment leading to treatment interruption within 1 cycle
- TEAEs leading to treatment interruption following 1 cycle / TEAEs related to study treatment leading to treatment interruption following 1 cycle
- TEAEs leading to dose reduction / TEAEs related to study treatment leading to dose reduction

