**PROGRAMMING NOTES:**

- Repeat Table 14.3-1.12
- Add footnote:

“TEAEs leading to treatment discontinuation: any TEAEs with Action taken with study treatment=Drug withdrawn after the first 28 days of study.”

“Related TEAE: TEAEs with causality=Related, Possibly Related or missing.”

Table 14.3-1.17 - Summary of Related Treatment-Emergent Adverse Events Leading to Treatment Discontinuation Following Cycle 1 Safety Analysis Set

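### Percentages of TEAEs leading to discontinuation, interruption or dose reduction within and following Cycle 1 share one all-treated denominator, so they cannot be read as early versus late risk

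*SAP*

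**What the plan says.** SAP 9.9.1 lists, for the overview table, separate early and late rows for TEAEs leading to discontinuation, interruption and dose reduction, including "TEAEs leading to treatment discontinuation following 1 cycle / TEAEs related to study treatment leading to treatment discontinuation following 1 cycle".

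The denominator follows from SAP 7.8, 8 and 9.9:

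- "All safety analyses will be performed on the Safety Analysis Set using descriptive statistics" (SAP 9.9).
- "The safety analysis set will consist of all patients who received at least one dose of study drug" (SAP 8). Reaching Cycle 2 is not a condition.
- "N will be the number of patients in the specified population and group" (SAP 7.8, N).
- "All summary percentages will be calculated using N, unless otherwise stated in a footnote" (SAP 7.8, Categorical data). The bullet on AEs repeats it: "while the percentages are calculated using N".

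Shell Table 14.3-1.1 sets the within and following rows under one N per group. The SOC/PT shells for each window repeat Table 14.3-1.12 with its N columns. Their added footnotes define only the window, as in Table 14.3-1.16 ("any TEAEs with Action taken with study treatment=Drug withdrawn after the first 28 days of study"), or relatedness. None sets another denominator. All of these tables are marked for the final analysis, which feeds an abbreviated CSR focused on safety (SAP 7.2).

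**The concern.** A reader who sees a within-Cycle-1 percentage next to a following-Cycle-1 percentage will take the pair as early against late toxicity. Two features of the layout prevent that reading.

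1. **Who is counted.** A patient permanently off ulixertinib by Day 28 can no longer have a late interruption, reduction or discontinuation, but stays in the denominator as event-free. Early exit is likely in this design. The first on-treatment tumour assessment is at Visit 5, Day 29 ± 3, and progression is a reason to stop treatment (Protocol 9.2), so some patients leave around the Cycle 1/2 boundary.
2. **How long each window lasts.** The first is capped at 28 days. The second runs for as long as the patient stays on drug.

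The first feature lowers the late percentage relative to the risk among patients still on drug. The second raises it with longer treatment. Retention may also differ across Groups 1 to 6, so comparisons of the late row between columns are affected too. The stakes are interpretive: Protocol 12.1.5.1 asks the SMC to look at later-cycle toxicities, and the final report centres on safety.

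**Working it through.** The plan states no percentage, event count or retention figure for these rows, so there is nothing to reproduce. The check isolates each effect with assumed inputs.

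**Step 1: denominator only.** Let x be patients with a late event, N the treated patients and m those still at risk after Day 28. The table shows x/N; the proportion among those at risk is x/m; the ratio is N/m. Take N = 38 (planned group size, SAP 6.4) and assume x = 4. The table always shows 4/38 = 10.5%.

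| m (assumed) | x/m |
|---|---|
| 38 | 10.5% |
| 34 | 11.8% |
| 30 | 13.3% |
| 27 | 14.8% |
| 23 | 17.4% |
| 19 | 21.1% |

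If every patient is still on drug after Day 28, there is no denominator effect.

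**Step 2: both effects, with risk held constant.** Assume an event rate λ = −ln(1 − 0.20) = 0.2231 per 28 days and exponential time on drug with rate μ = ln 2 / median (in cycles), independent of the events.

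- Within Cycle 1, on N: λ/(λ+μ) × [1 − exp(−(λ+μ))]
- Still on drug after Day 28: exp(−μ)
- Following, among those at risk: λ/(λ+μ)
- Following, on N: exp(−μ) × λ/(λ+μ)

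For a median of 2 cycles, μ = 0.3466 and λ+μ = 0.5697. Within = 0.3917 × 0.4343 = 17.0%. Still on drug = 70.7%. Following on N = 0.7071 × 0.3917 = 27.7%.

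| Median cycles on drug | Within, on N | Still on drug after Day 28 | Following, on N | Following, at risk |
|---|---|---|---|---|
| 1.5 | 16.2% | 63.0% | 20.5% | 32.6% |
| 2 | 17.0% | 70.7% | 27.7% | 39.2% |
| 3 | 17.9% | 79.4% | 39.0% | 49.1% |
| 5 | 18.7% | 87.1% | 53.7% | 61.7% |

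Risk is identical in both windows, yet the late row runs from 20.5% to 53.7% with time on drug alone. The at-risk percentage moves further from the within figure, because it does nothing about window length.

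**Step 3: does a rate repair it?** Divide patients with a first event in the period by time on drug in the period up to that event. At a median of 2 cycles:

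- Within: time = 0.4343/0.5697 = 0.7623 cycles per treated patient; 0.1701/0.7623 = 0.2231.
- Following: time = 0.7071/0.5697 = 1.2412 cycles; 0.2770/1.2412 = 0.2231.

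Both return λ. In the SAP's months of 30.4375 days this is 0.2231 × 30.4375/28 = 0.243 per patient-month. The clock must stop at the first event. With all time on drug in the denominator (0.8451 and 2.0403 cycles), the rates would be 0.201 and 0.136, which are unequal despite constant risk.

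**The case against.** The case for leaving the tables alone is substantial.

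- **x/N is legitimate.** It is the crude share of treated patients with a late event, in a descriptive analysis with no test between windows planned. The SAP never calls it a risk among patients still on drug. A reader might infer that the SAP contradicts itself or uses a wrong denominator; the documents do not support that, because the N rule is explicit and consistently applied.
- **Replacing the denominator would be worse.** A reader might infer that the late rows should simply be divided by patients with a dose on or after Day 29. Under constant risk that turns 17% against 28% into 17% against 39%. Discontinuation essentially happens once per patient, so its early and late rows add up to the total under one N, and this would be lost. The rule can also drop a patient who is in the numerator. Protocol 8.1.3 ends treatment when a delay exceeds 21 days, so someone last dosed on Day 15 and then held reaches that limit after Day 28 with no later dose.
- **The model does not fit every endpoint.** Step 2 suits interruptions and reductions; discontinuation itself ends exposure.
- **Much of the information is elsewhere.** Table 14.1-4.1 gives cycles received and exposure, and Listings 16.2.5-3 and 16.2.7-2 give patient-level exposure and event dates. All are in the final analysis.

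A reader might also point to visit frequency: "Cycle 3 and subsequent cycles have one scheduled visit per cycle" (Protocol 10.3.3). That adds nothing here. Protocol 10.4.4 has staff ask about events since the previous visit and record start dates.

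The first three objections stand and shape the fix. The fourth stands in part: the SAP does not link exposure to the AE tables, and a reader would have to build rates by hand from listings.

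**Conclusion.** The point holds as a matter of presentation and interpretation. It is not an error in the plan. Both windows use the full Safety Analysis Set per group, no shell footnote changes this, and the following rows therefore mix event risk with how many patients remained and for how long.

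The actual size cannot be computed from the documents. The figures of 17% against 28% (median 2 cycles) and 19% against 54% (median 5 cycles) rest on an assumed constant 20% risk per 28 days and exponential time on drug independent of events. A reader might infer that the late percentages are biased in a known direction as a measure of early-versus-late risk. They are not: the denominator pulls the late row down, the open-ended window pushes it up, and the net effect depends on retention. An inexpensive addition before the final tables are run is justified.

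**What to change.** 1. Keep the x/N percentage in every table.
2. In SAP 9.9.1 and Table 14.3-1.1, add for both periods the number of patients at risk. For the within rows this is N. For the following rows it is patients not permanently discontinued from ulixertinib by Day 28, which keeps the held-then-withdrawn patient in.
3. In the same table, add for both periods patients with a first such event in the period per patient-month on drug in that period, with time stopping at the first event.
4. In Tables 14.3-1.16, -1.17, -1.22, -1.23, -1.28 and -1.29, show the at-risk number and add a footnote that x/N is not a risk among patients still on drug.
5. Correct two shell errors in the same family. The within-Cycle-1 Table 14.3-1.21 carries a footnote that places its events after the first 28 days. Table 14.3-1.22 is titled as related events in its shell but not in the output list.

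The cost is a few rows, some footnotes and one derived count. The SAP's exposure formulas already use first and last dosing dates, so no new data are needed. The downside to accept is that late toxicity may look less favourable.

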### 9.9.2 *Clinical Safety Laboratory Evaluation*

All haematology, biochemistry, and urinalysis laboratory tests collected will be reported.

The numerical measurements and change from baseline of all haematology, biochemistry, and urinalysis laboratory tests will be summarized using descriptive summary statistics for each visit.

For laboratory tests covered by the NCI-CTCAE (version 5), laboratory data will be graded accordingly. 'Normal' will be assigned for all non-missing values not graded as 1 or higher. For laboratory tests where grades are not defined by NCI-CTCAE, results will be graded by the low/normal/high classifications based on laboratory normal ranges as collected in the CRF. Separate tables will be created for Graded and Non-gradable laboratory values.

Haematology and biochemistry laboratory tests will be summarized by:

- Tables (Gradable and Non-gradable) to describe the worst on-treatment value by cycle.
- Shift tables (Gradable and Non-gradable) to compare baseline to the worst on-treatment value.

Listings of all laboratory data with values flagged to show the corresponding NCI-CTCAE grades and the classifications relative to the laboratory normal ranges will also be provided. Also results of serum pregnancy tests will be listed.

### 9.9.3 *Other Safety data*

#### 9.9.3.1 *Vital signs*

Vital signs include the following parameters: systolic blood pressure (SBP) (mmHg), diastolic blood pressure (DBP) (mmHg), pulse (beats/min), and temperature (°C).

The numerical measurements and change from baseline of all vital signs parameters will be summarized using descriptive summary statistics for each visit.

Shift tables of baseline to worst on-treatment result (low, normal, high, very high) will be presented.

**Table 7. Thresholds for classification of vital signs test results**

Vital Sign	Criteria	Flag
Temperature	< 36.4°C	Low
	36.4°C – 37.7°C	Normal
	> 37.7°C	High
Pulse	< 55 bpm	Low
	55-100 bpm	Normal
	101-150 bpm	High
	> 150 bpm	Very High
Systolic Blood Pressure	< 90 mmHg	Low
	90-130 mmHg	Normal
	131-160 mmHg	High
	≥ 161 mmHg	Very High
Diastolic Blood Pressure	< 60 mmHg	Low
	60-85 mmHg	Normal
	86-100 mmHg	High
	≥ 101 mmHg	Very High

All Vital Signs will be Listed.

#### 9.9.3.2 *Electrocardiogram (ECG)*

ECG includes the following parameters: Heart Rate (beats/min), PR Interval (msec), QRS Duration (msec), RR Interval (msec), QT Interval (msec), and QT interval corrected for heart rate by the Fridericia's formula (QTcF) Interval (msec).

The numerical measurements at baseline of all ECG parameters will be summarized using descriptive summary statistics.

A listing of ECG evaluations will be created.

#### 9.9.3.3 *ECHO/MUGA*

ECHO/MUGA assessments at baseline will be summarized using descriptive summary statistics.

A listing of ECHO/MUGA evaluations will be created.

#### 9.9.3.4 *Physical Examination*

Physical Examination includes the following parameters: HEENT, Thorax, Abdomen, Skin and Mucosae, Neurological, Extremities, Urogenital, General Appearance, Heart, Back, and Lymph Nodes.

All physical examination assessments at baseline will be summarized using descriptive summary statistics.

A listing of physical examination evaluations will be created.

#### 9.9.3.5 *Ophthalmology exam*

A listing of ophthalmological examination assessments will be created.

#### 9.9.3.6 *ECOG Performance status*

The number and percentages of patients will be tabulated for ECOG performance score categories at each visit.

A listing of all ECOG Performance status at all visits will be presented.

## 10 Interim Analyses

No interim analysis is planned. The outputs provided for the regular SMC data reviews are covered in a separate SAP.

## 11 Changes to Planned Analyses

No major changes to analyses planned in the protocol are expected.

A new analysis population was defined to further investigate efficacy. Although the SAP will be signed and finalized prior to the first study analysis, this new analysis population is for exploratory purposes only.

Demographic and baseline data was planned in the Protocol to be reported for all analysis populations. However, at least for Part A, this will only be reported on FAS. For Part B, this may

be revised and additional tables may be added for each analysis set.

## 12 Document History

Date	Version	Modified by	Brief details of changes made to template
20Dec2021	1.0	[name]	First SAP Version.
09Jun2023	2.0	[name]	Updated version of the SAP to cover for the dry-run comments and to account for the required updates due to the study being early terminated.

## 14 Appendices

### 14.1 *Schedule of events*

**Table 14.1 Part A and B: Schedule of Activities**

		Cycle 1 Day 1 through 28			Cycle 2 Day 29 through 56			Cycle 3-X 28-day cycles, visit on 1 st day of cycle	Post Treatment Period		
Visit	1 Screening	2 Baseline	3 Tx	4 Tx	5 Tx	6 Tx	7 Tx	8 -X Tx	End of Treatment (EOT) Visit	Safety Follow- Up a	Follow- Up b
Visit Day	-28 to -1	1 ± 0	8 ± 3	15 ± 3	29 ± 3	36 ± 3	43 ± 3	57 ± 3	≤14 ± 3 days after last dose	30 ± 3 days after last dose	
Informed consent	X										
Inclusion/exclusion criteria	X	X									
Demography	X										
Medical history c	X	X	X	X	X	X	X	X	X		
Cancer history d	X										X
Concomitant medications	X	X	X	X	X	X	X	X	X		
Measure height	X										
Measure weight	X	X	X	X	X	X	X	X	X		
Vital signs	X	X	X	X	X	X	X	X	X		
Physical examination e	X										
ECOG	X	X	X	X	X	X	X	X	X		
Ophthalmology exam f	X										
Pregnancy test g,h	X	X g			X h			X h	X h		
Clinical lab tests i,j	X	X i	X	X	X	X	X	X j	X		
Electrocardiogram (ECG) k	X										
ECHO cardiogram or MUGA	X										

**Table 14.1 Part A and B: Schedule of Activities**

		Cycle 1 Day 1 through 28			Cycle 2 Day 29 through 56			Cycle 3-X 28-day cycles, visit on 1 st day of cycle	Post Treatment Period		
Visit	1 Screening	2 Baseline	3 Tx	4 Tx	5 Tx	6 Tx	7 Tx	8 -X Tx	End of Treatment (EOT) Visit	Safety Follow- Up a	Follow- Up b
Assess current disease status l	X				X			X	X		X m
Study drug administration n		X		X							
Adverse events (AEs)		X	X	X	X	X	X	X	X	X	
Obtain unused drug			X	X	X	X	X	X	X		
Compliance by pill count			X	X	X	X	X	X	X		
Study drug dispensed		X	X	X	X	X	X	X			
Part A Only											
Tissue biopsy, if indicated o,p	X o				X				X p		
Pharmacodynamic blood samples q		X		X							
ctDNA r		X		X	X				X		
Pharmacokinetic samples s				X s							
Part B Only											
Randomization	X										

Table footnotes:

a Patients will return to the clinic or will be contacted for a safety follow-up assessment 30 days  $\pm$  3 days after the last dose of study drug was taken; or earlier if subsequent therapy for advanced malignancy is initiated prior to 30 days  $\pm$  3 days.

- b Patients or their legally authorized representatives will be contacted every three months ( $\pm$  7 days) until death, end of the study, or patient withdrawal of consent, whichever comes first. Survival and subsequent treatment status may be collected by public records, medical records, or by contacting the patient or their legally authorized representative by phone.
- c Full medical history at screening, only review/update of history at subsequent visits.
- d Oncologic history of the malignancy under study including prior regimens (duration of therapy, best response on therapy, date of discontinuation, and reason for discontinuation), surgery, and radiation therapy.
- e Physical examinations should be symptom driven after the Screening Visit.
- f Ophthalmological examinations will be performed by an ophthalmologist at screening, and whenever clinically indicated. In Part B, only patients in the uleritinib arm need an ophthalmological exam. See section 10.1.5 for a full description of tests.
- g ONLY if the screening serum pregnancy test was performed more than 1 day previously.
- h After screening and baseline, if urine pregnancy test is positive, confirm with serum test.
- i Visit 2 clinical lab samples should be collected pre-dose if not done during Screening Visit within 72 hours of start of treatment.
- j Chemistry, hematology, and urinalysis. After Cycle 2, clinical labs to be performed prior to starting each new cycle or more frequently when clinically indicated at the investigator's discretion. See section 10.1.6 for a full description of test.
- k Patients with a normal ECG in Cycle 1 do not need to have repeat ECGs in subsequent cycles. Patients should be supine for 5 minutes prior to the ECG.
- l Tumor assessments will be made prior to dose initiation, at Visit 5, and then every 2 cycles. Patients who discontinue treatment for reasons other than progression will have assessments at the EOT visit (unless their previous assessment was performed within 28 days). The same imaging modality used for an individual patient (i.e. CT or MRI) at Screening should be maintained throughout the study.
- m Patients that discontinue study treatment for any reason other than disease progression, must continue to have disease assessments every 8 weeks ( $\pm$  7 days) until disease progression or the initiation of subsequent anticancer therapy.
- n Study drug to be taken twice daily. The first dose should be taken in the clinic on days when PD sampling occurs i.e., Cycle 1/Visit 2 (Day 1) and Cycle 1/Visit 4 (Day 15), remaining doses on all other days to be self-administered by patient.
- o Tissue biopsy for Part A only. If a patient has undergone a biopsy within  $\leq$  6 months and has not received any anticancer treatment since undergoing the biopsy, archival tissue from this biopsy may be used to fulfill screening tissue requirements.
- p Tissue biopsy at final study visit/at progression is optional, but strongly encouraged to help elucidate mechanism of resistance.
- q Collect pre-dose and 4 hour +/- 10 mins post-dose blood samples for PD.

**Sponsor:** BioMed Valley Discoveries

**Protocol:** BVD-523-ABC

